3.7. Data Handling Conventions and Transformations

The following conventions will be used for the imputation of date of birth when it is partially missing or not collected:

- If only month and year of birth is collected, then "15" will be imputed as the day of birth
- If only year of birth is collected, then "01 July" will be imputed as the day and month of birth
- If year of birth is missing, then date of birth will not be imputed.

In general, age collected on Day 1 (in years) will be used for analyses and presented in listings. If age on Day 1 is not available for a participant, then age derived based on date of birth and the Day 1 visit date will be used instead. If an enrolled participant was not dosed with any study drug, the enrollment date will be used instead of the Day 1 visit date. For participant without an enrollment date the first informed consent was signed will be used for the age derivation. Age required for longitudinal and temporal calculations and analyses (eg, estimates of creatinine clearance, age at date of AE) will be based on age derived from date of birth and the date of the measurement or event, unless otherwise specified.

Non-PK data that are continuous in nature but are less than the lower limit of quantitation (LOQ) or above the upper LOQ will be imputed as follows:

- A value that is 1 unit less than the lower LOQ at the same precision level of the originally reported value will be used to calculate descriptive statistics if the datum is reported in the form of "< x" (where x is considered the lower LOQ). For example, if the values are reported as < 50 and < 5.0, values of 49 and 4.9, respectively, will be used to calculate summary statistics. An exception to this rule is any value reported as < 1 or < 0.1, etc. For values reported as < 1 or < 0.1, a value of 0.9 or 0.09, respectively, will be used to calculate summary statistics.
- A value that is 1 unit above the upper LOQ will be used to calculate descriptive statistics if the datum is reported in the form of "> x" (where x is considered the upper LOQ). Values with decimal points will follow the same logic as above.
- The lower or upper LOQ will be used to calculate descriptive statistics if the datum is reported in the form of " \leq x" or " \geq x" (where x is considered the lower or upper LOQ, respectively).

If methods based on the assumption that the data are normally distributed are not adequate, analyses may be performed on transformed data (eg, change from baseline in HIV-1 RNA will be performed on the \log_{10} transformed data) or nonparametric analysis methods may be used, as appropriate.

Data Handling for PK Summaries

Natural logarithm transformation will be used for analyzing non-BLQ concentrations and PK parameters in intensive PK samples. Concentration values that are below the limit of quantitation (BLQ) will be presented as "BLQ" in the concentration data listing. Values that are BLQ will be treated as 0 at predose and postdose time points for summary purposes. The number of samples will be summarized to reflect the actual number of samples assessed at that time point

At predose, if all concentration values are BLQ, then the mean, and order statistics (minimum, Q1, median, Q3, and maximum) will be displayed as 0 and the rest of the summary statistics (ie, SD and CV) will be missing. If any values are non-BLQ, then the number of samples, order statistics, and all summary statistics will be displayed.

At any given postdose time point, if more than one-third of the participants have a concentration value of BLQ, then only the number of samples and order statistics will be displayed; otherwise, order statistics and summary statistics will be displayed.

The following conventions will be used for the presentation of order statistics for intensive PK concentrations:

- If at least 1 participant has a concentration value of BLQ for the time point, the minimum value will be displayed as "BLQ."
- If more than 25% of the participants have a concentration data value of BLQ for a given time point, the minimum and Q1 values will be displayed as "BLQ."
- If more than 50% of the participants have a concentration data value of BLQ for a given time point, the minimum, Q1, and median values will be displayed as "BLQ."
- If more than 75% of the participants have a concentration data value of BLQ for a given time point, the minimum, Q1, median, and Q3 values will be displayed as "BLQ."
- If all participants have concentration data values of BLQ for a given time point, all order statistics (minimum, Q1, median, Q3, and maximum) will be displayed as "BLQ."

Concentration related PK parameters (eg, C_{last} , C_{max} , and C_{tau}) that are BLQ will be excluded before log transformation or statistical model fitting and displayed as described above.

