1.3. Sample Size and Power

A sample size of 6 to 8 participants in each dose cohort will provide 83% to 94% power to detect a treatment difference of $1.0 \log_{10} \text{copies/mL}$ in change from baseline in HIV-1 RNA on Day 11 between at least one of the study drug dose groups and the historical placebo group (N = 21). In this power analysis, it is assumed that a standard deviation (SD) for the change from baseline in

HIV-1 RNA on Day 11 is 0.662 log₁₀ copies/mL for each study drug dose group and 0.359 log₁₀ copies/mL for the placebo group, and a 2-sided t-test is conducted at an alpha level of 0.05. Standard deviations were estimated from historical Phase 1b studies conducted by the sponsor (GS-US-120-0104, GS-US-141-1219, and GS-US-200-4072). The maximum SD from treatment groups was used for the study drug dose group and SD from the pooled placebo group was used for the placebo group.

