2.2. Dose Escalation Analysis

A safety review team (SRT) will review the data from this substudy after all participants from Cohort 1 complete their Day 11 visit. The SRT review will include cumulative safety and HIV-1 RNA data through the primary endpoint (Day 11) and available PK data from Cohort 1 of this substudy; and/or relevant and available safety and PK data from the Phase 1a FIH study for GS-6212 (as appropriate). This initial SRT review will facilitate decision-making for dose level, dosing regimen (including whether GS-6212 study drug will be taken in a fasted state, or with a low-fat or high-fat meal) and timing of dosing for Cohorts 2 to 5. Following SRT review of Cohort 1, no additional cohorts were required. Cohorts 2-5 were not enrolled.

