6. EFFICACY ANALYSES

6.1. Primary Efficacy Endpoint

The primary efficacy endpoint is the change from baseline in plasma HIV-1 RNA (log₁₀ copies/mL) on Day 11.

Historical HIV-1 RNA data for placebo participants from 3 sponsor Phase 1b studies (GS-US-120-0104, GS-US-141-1219, and GS-US-200-4072) will be combined to form a single placebo group for the purpose of HIV-1 RNA analysis through Study Day 11. For Study GS-US-200-4072, HIV-1 RNA (log₁₀ copies/mL) collected on Day 10 will be used for "Day 11" since HIV-1 RNA was not collected on Day 11 for this study. GS-6212 cohort will be compared to the pooled placebo group with respect to the primary efficacy endpoint, the change from baseline in plasma HIV-1 RNA (log₁₀ copies/mL) on Day 11, using the 2-sided t-test conducted at an alpha level of 0.05. The analysis will be conducted using the FAS.

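### Section 3.7 leaves the primary HIV-1 RNA t-test open to replacement by an unnamed nonparametric test; under the planning SDs neither a rank-sum fallback nor the Appendix 2 code holds 5%

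*SAP*

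**What the plan says.** Section 6.1 compares the GS-6212 cohort with pooled historical placebo on the primary endpoint "using the 2-sided t-test conducted at an alpha level of 0.05". It does not say whether the variances are pooled or separate. Sections 6.2.1, 6.3 and 6.4 carry the same method to Day 8, to the maximum reduction and to the sensitivity analyses.

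Section 3.7 is a general paragraph on data handling. If normal-theory methods are not adequate, it allows either transformed data or a switch: "nonparametric analysis methods may be used, as appropriate". Its example of a transformation is the primary variable itself: "eg, change from baseline in HIV-1 RNA will be performed on the" log10 scale.

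Section 2.2 puts Day 11 HIV-1 RNA within the scope of the safety review team's review, and then reports in the past tense: "Following SRT review of Cohort 1, no additional cohorts were required". The signatures at the end of the SAP are dated 28 August 2024. Section 1.2 describes the substudy as open-label.

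Appendix 2 gives the code for the p-values: PROC MIXED with treatment as the only effect and no group-specific residual variance. For two groups this is the pooled-variance t-test.

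**The concern.** The plan has one formal primary test in one cohort, and its value lies in being fixed in advance at a known error rate. Section 3.7 leaves that test open: nobody can say from the text when the switch would be made or to what. The transformation route is already used up, because the endpoint is on the log10 scale, so for this endpoint the clause leaves only the nonparametric route. When the SAP was signed, the safety review of the only cohort had taken place, with Day 11 HIV-1 RNA in its stated scope.

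The usual nonparametric choice, the Wilcoxon rank-sum test, is also not a safe default here. It is sensitive to unequal spread when the smaller group is the more variable one, and the planning values describe exactly that situation. A statement of significance at 0.05 might then not carry a 5% error rate.

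**Working it through.** **Inputs (Section 1.3).** "A sample size of 6 to 8 participants in each dose cohort"; 21 historical placebo participants; SD 0.662 (active) and 0.359 (placebo); difference 1.0 log10 copies/mL; 2-sided alpha 0.05. On the origin of 0.662: "The maximum SD from treatment groups was used for the study drug dose group".

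**Step 1: which t-test gives the stated power?** With separate variances, SE = √(s₁²/n₁ + s₀²/n₀), with Satterthwaite degrees of freedom and power from the noncentral t.

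- n = 6: SE = √(0.662²/6 + 0.359²/21) = √(0.0730 + 0.0061) = 0.281; noncentrality 1.0/0.281 = 3.55; df 5.87; power 83.6%.
- n = 8: SE = √(0.0548 + 0.0061) = 0.247; noncentrality 4.05; df 8.62; power 94.6%.

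These agree with the stated 83% and 94%. The pooled formula gives over 99%, and a normal approximation gives 94 to 98%. The sample size therefore rests on the separate-variance test.

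**Step 2: what the common-variance code does.** The pooled variance weights the large, less variable placebo group most heavily.

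- n = 6: pooled SD = √[(5 × 0.662² + 20 × 0.359²)/25] = 0.437; assumed SE = 0.437 × √(1/6 + 1/21) = 0.202, against a true 0.281.
- n = 8: pooled SD = √[(7 × 0.662² + 20 × 0.359²)/27] = 0.457; assumed SE = 0.457 × √(1/8 + 1/21) = 0.190, against a true 0.247.

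The standard error is understated, so the test rejects too often.

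**Step 3: rejection rate with no mean difference.** Normal data, planning SDs, 200,000 simulated trials per cohort size, nominal 5%:

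| Test | n = 6 | n = 7 | n = 8 |
|---|---|---|---|
| t-test, separate variances | 5.3% | 5.2% | 5.3% |
| Rank-sum, exact or uncorrected normal | 9.9% | 9.2% | 8.7% |
| Rank-sum, continuity-corrected normal | 8.9% | 9.2% | 8.7% |
| Rank-sum, t approximation | 7.9% | 7.5% | 7.2% |
| t-test, common variance (Appendix 2) | 15.5% | 14.3% | 13.1% |

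Repeat runs gave rank-sum values down to 8.6% at n = 8.

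**Step 4: dependence on the active SD.** An SD of 0.5 is an assumed intermediate value; at it, the continuity-corrected rank-sum test rejects about 6.7%. With 0.359 in both groups, the exact test gives 4.9% (n = 6) and 4.7% (n = 8), and the common-variance t-test returns to about 5%.

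**Step 5: effect of a free choice.** Taking the smaller p-value of the separate-variance t-test and the continuity-corrected rank-sum test gives 9.3% (n = 6) and 8.9% (n = 8) under the planning SDs. Choosing between the coded test and rank-sum gives 13.8 to 16.2%, most of it from the coded test. If the switch were made strictly on a Shapiro-Wilk result, starting from the separate-variance test, the rate would be only 5.7 to 6.1%.

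**The case against.** The strongest reply is that the specific text governs. Section 6.1 names the t-test and Appendix 2 codes it, while Section 3.7 is a general convention whose only HIV-1 RNA example is a transformation already in use. That makes a switch a permission and not a plan, but the permission does cover this endpoint and has no limits.

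A reader might infer that the fallback is worse than the test it replaces and nearly doubles the error rate. That holds only against the separate-variance t-test, which neither Section 6.1 nor Appendix 2 specifies. Against the coded test, a move to rank-sum would lower the error rate under the planning SDs.

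A reader might also infer that the test was picked after the results were known. The SAP shows opportunity only: the review came before the final text, and nothing indicates that any result guided the choice of method.

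The figures are also conditional. Rank-sum is assumed, because no test is named. The 0.662 is the largest SD among historical treatment groups, and a drug without effect might well show the placebo SD. The simulation uses normal data, although the clause applies when normality is in doubt. Each of these stands, which is why a range is needed.

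Finally, this is a proof-of-concept study without multiplicity adjustment. At a true difference of 1.0 and n = 6, the tests reject in about 83% (separate variances), 92% (rank-sum) and 98% (common variance) of trials, so a strong effect would probably be found by any of them. This limits the practical consequence but does not make the stated 5% level correct.

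**Conclusion.** The point holds in a limited form. Section 3.7 leaves the primary test replaceable without a criterion or a named alternative, in a document finalised after the review of the only cohort. By itself that would be little more than missing detail. It matters because, under the SAP's own planning SDs, only the test behind the power statement keeps its level (about 5%). A rank-sum fallback would run at about 8.6 to 9.9%, or 7.2 to 7.9% with a t approximation, and the coded common-variance test at about 13 to 15%.

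The inflation depends on the active group being more variable than placebo when there is no mean difference; it shrinks as the SDs converge and is absent when they are equal. The coded variance assumption is the larger of the two problems, and one change settles both.

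**What to change.** - **Sections 3.7 and 6.1:** state that the HIV-1 RNA change endpoints (Sections 6.1, 6.2.1, 6.3 and 6.4) are always analysed on the log10 scale by the 2-sided t-test with separate group variances, whatever the observed distribution, and that the Section 3.7 switch does not apply to them.
- **Appendix 2:** align the code, for example by adding a group-specific residual variance (`repeated / group=trt`) with Satterthwaite or Kenward-Roger degrees of freedom.
- **Any nonparametric analysis:** name it now, choose one that tolerates unequal variances (for example a studentised permutation test or Brunner-Munzel), report it beside the primary result, and never let it replace that result.

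The cost is a few sentences and one line of code. The sponsor gives up the freedom to switch tests. It also accepts a less favourable p-value than the common-variance code would give if the active group is the more variable one. Planned power does not change, because the stated 83 to 94% already belongs to the separate-variance test. If the SAP can no longer be revised, Section 1 provides for documenting later changes in the clinical study report; the separate-variance result should then be shown there beside the coded one.

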3.8. Analysis Visit Windows

3.8.1. Definition of Predose, Postdose, Study Day

Study day will be calculated from the first dosing date of study drug (or first dose date of placebo for placebo historical control group [HIV-1 RNA data only]) and derived as follows:

- For postdose study days: Assessment Date First Dosing Date + 1
- For days prior to the first dose: Assessment Date First Dosing Date

Therefore, study day 1 is the day of first dose of study drug administration.

Baseline is defined as the last available value collected on or prior to the first dose date (and time, where applicable) of study drug (ie, prior to taking first dose of study drug). Postbaseline is defined as any value collected after the first dose of study drug. Last Study Date is the latest of clinic visit dates and laboratory visit dates, including all follow-up visits for participants who prematurely discontinued study or who completed study according to the Study Completion eCRF.

3.8.2. Analysis Visit Windows

Participant visits might not occur on protocol-specified days. Therefore, for the purpose of analysis, observations will be assigned to analysis windows.

The analysis windows for HIV-1 RNA are provided in Table 3-1; for hematology, chemistry, urinalysis, and eGFR_{CG} in Table 3-2; for vital signs and weight in Table 3-3; for ECGs and coagulation in Table 3-4; and CD4 cell count and percentage in Table 3-5.

Table 3-1. Analysis Visit Windows for HIV-1 RNA

		Visit Window Study Day	
Nominal Visit	Nominal Study Day	Lower Limit	Upper Limit
Baseline	1	(none)	1
Day 2	2	2	2
Day 3	3	3	3
Day 4	4	4	5
Day 7	7	6	7
Day 8	8	8	8
Day 9	9	9	9
Day 10	10	10	10
Day 11	11	11	11
Day 25	25	12	(none)

Cohort GS-6212 will be compared to the historical placebo control group through Study Day 11.

The percentage of participants with HIV-1 RNA < 50 copies/mL will be displayed on Day 11 (last value prior to starting standard of care) and on Days 25.

Table 3-2. Analysis Visit Windows for Hematology, Chemistry (including Thyrotropin), Urinalysis and $eGFR_{CG}$

		Visit Window Study Day	
Nominal Visit	Nominal Study Day	Lower Limit	Upper Limit
Baseline	1	(none)	1
Day 3	3	2	5
Day 7	7	6	9
Day 11	11	10	11
Day 25	25	12	(none)

Table 3-3. Analysis Visit Windows for Vital Signs and Weight

		Visit Window Study Day	
Nominal Visit	Nominal Study Day	Lower Limit	Upper Limit
Baseline	1	(none)	1
Day 2*	2	2	2
Day 3	3	3	3
Day 4*	4	4	5
Day 7	7	6	9
Day 11	11	10	11
Day 25	25	12	(none)

^{*}Weight is not scheduled to be collected on Day 2 and Day 4 per protocol, so any weight collected on Day 2 will be considered for Day 3, any weight collected during Day 4 period will be considered for Day 7.

Table 3-4. Analysis Visit Windows for ECGs and Coagulation Tests

		Visit Window Study Day	
Nominal Visit	Nominal Study Day	Lower Limit	Upper Limit
Baseline	1	(none)	1
Day 7	7	2	9
Day 11	11	10	11
Day 25	25	12	(none)

		Visit Window Study Day	
Nominal Visit	Nominal Study Day	Lower Limit	Upper Limit
Baseline	1	(none)	1
Day 11	11	2	11
Day 25	25	12	(none)

Table 3-5. Analysis Visit Windows for CD4 Cell Count and Percentage

3.8.3. Selection of Data in the Event of Multiple Records in an Analysis Visit Window

Depending on the statistical analysis method, single values may be required for each analysis window. For example, change from baseline by visit usually requires a single value.

If multiple valid, nonmissing measurements exist in an analysis window, records will be chosen based on the following rules if a single value is needed:

- For baseline, the last nonmissing value on or prior to the first dose of study drug will be selected, unless specified differently. If there are multiple records with the same time or no time recorded on the same day, the baseline value will be the average of the measurements for continuous data (except for HIV-1 RNA, see below), or the measurement with the lowest severity (ie, normal will be selected over abnormal for safety ECG findings) for categorical data.
- For postbaseline values:
 - The record closest to the nominal day for that visit will be selected (with the exception of CD4+ cell count and CD4% in which the latest record will be selected and HIV-1 RNA level [see below]).
 - If there are 2 records that are equidistant from the nominal day, the later record will be selected.
 - If there is more than 1 record on the selected day, the average will be taken for continuous data (except for HIV-1 RNA, see below) and the worst severity will be taken for categorical data, unless otherwise specified.
- For baseline and postbaseline HIV-1 RNA, the latest (considering both date and time) record(s) in the window will be selected. If both "Roche COBAS 6800" and "Roche COBAS 6800 Repeat" (ie, the HIV-1 RNA result obtained from an additional aliquot of the original sample) are available with the same collection time, the results from the "Roche COBAS 6800 Repeat" will be selected for analysis purposes; otherwise, if there are multiple "Roche COBAS 6800" records with the same collection time, the geometric mean will be taken for analysis purposes.

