7.1.7.1. Summaries of AE Incidence in Combined Severity Grade Subsets

A brief, high-level summary of the number and percentage of participants who experienced at least 1 TEAE in the categories described below will be provided for events with an onset date up to Day 11 (prior to adding SOC) and for the entire study.

- TEAEs
- TEAEs with Grade 3 or higher
- TEAEs with Grade 2 or higher
- TE treatment-related AEs
- TE procedure-related AEs
- TE treatment-related AEs with Grade 3 or higher
- TE treatment-related AEs with Grade 2 or higher

- TE SAEs
- TE treatment-related SAEs
- TEAEs leading to premature discontinuation of study drug
- TEAEs leading to premature discontinuation of study
- TEAEs leading to death (ie, outcome of death)

The number and percentage of participants who experienced at least 1 TEAE will be provided and summarized by SOC, PT:

- TEAEs, by maximum severity
- TEAEs up to Day 11, by maximum severity
- TEAEs with Grade 3 or higher, by maximum severity
- TE treatment-related AEs, by maximum severity
- TE procedure-related AEs, by maximum severity
- TE treatment-related AEs with Grade 3 or higher, by maximum severity
- TE SAEs
- TE treatment-related SAEs
- TEAEs leading to premature discontinuation of study

Multiple events will be counted only once per participant in each summary. Adverse events will be summarized and listed first in alphabetic order of SOC and then by PT in descending order of total frequency within each SOC. For summaries by severity grade, the most severe grade will be used for those AEs that occurred more than once in an individual participant during the study.

In addition to the above summary tables, all TEAEs and TE treatment-related AEs will be summarized by PT only, in descending order of total frequency.

In addition, data listings will be provided for the following:

- All AEs, indicating whether the event is treatment emergent
- All SAEs
- All Deaths

- All AEs with severity of Grade 3 or higher
- All AEs leading to premature discontinuation of study drug or study

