12. APPENDICES

Appendix 1. Study Procedures Table

Study Procedure	Screeninga	D1b	D2	D3	D4	D 7	D8	D9	D10	D11b	D25	ETc
Visit Window											±2D	
Written informed consent	X											
Medical history and demography	X											
Complete physical examination	X	X									X	X
Symptom-driven physical examination ^d			X		X	X				X		
Height	X											
Weight	X	X		X		X				X	X	X
Vital signse	X	X	X	X	X	X				X	X	X
HBV blood panel and HCV serology ^f	X											
CD4 cell count ^f	X	X								X	X	X
Plasma sample for HIV-1 genotyping/phenotyping ^{f,g}	X	X								Х		
Plasma HIV-1 RNAf	X	X	X	X	X	X	X	X	X	X	X	X
Hematology ^f	X	X		X		Х				X	X	X
Coagulation panelf	X	X				X				X	X	X
Chemistry ^f	X	X		X		X				X	X	X
Urinalysis ^f	X	X		X		X				X	X	X
Serum pregnancy test ^{f,h}	X											
Urine pregnancy test ^{fh,i}		X									X	X
Serum FSH ^{fj}	X											
12-Lead ECG	X	X				X				X	X	X
Intensive plasma PKk		X							X			
Single trough plasma PK ¹			X	X	X	X	X	X		X		X
Review AEs and concomitant medications ^m	X	X	X	X	X	Х	X	X	X	X	X	X
Study drug (GS-6212) dispensation ⁿ		X										
Study drug (GS-6212) dosing ^{o, p}		X	X	X	X	X	X	X	X			
BVY dispensation, as applicable										X		

Study Procedure	Screening ^a	D1 ^b	D2	D3	D4	D 7	D8	D9	D10	D11b	D25	ET
Visit Window											±2D	
BVY or an alternative SOC administration										Xq	őř	-

AE = adverse event; AM = before noon; BVY = bictegravir/emtricitabine/tenofovir alafenamide (B/F/TAF; coformulated; Biktarvy®); CD4 = clusters of differentiation 4; D = Day; ECG = electrocardiogram; eCRF = electronic case report form; ET = early termination; FSH = follicle-stimulating hormone; HBV = hepatitis B virus; HCV = hepatitis C virus; HIV-1 = human immunodeficiency virus type 1; PK = pharmacokinetic(s); RNA = ribonucleic acid; SAE = serious adverse event; SOC = standard of care

- a Prospective participants should be screened no more than 28 days prior to administration of the first dose of study drug.
- b Overnight fasting (≥ 6 hours prior to dosing) is required.
- c ET assessments will be performed within 72 hours of prematurely discontinuing from the study or study drug, as applicable.
- d Symptom-driven physical examinations will be performed as needed, based on reported signs and symptoms.
- e Vital signs include blood pressure, heart rate, respiration rate, and body temperature. Participants should be sitting down for 5 minutes before vital sign measurements are obtained.

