- q After assessments on Day 11 or upon ET, participants will initiate a regimen of BVY provided by the sponsor or an alternative SOC ART regimen selected by the investigator. Participants who discontinue study drug before Day 11 should start this regimen at the time of discontinuation (see Section 6.4.1 of the master protocol).

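### Data labelled as pre-SOC are selected by calendar study day alone, so HIV-1 RNA, AE and laboratory data collected after an early start of Biktarvy/SOC can count as GS-6212 monotherapy data

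*SAP*

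**What the plan says.** **The label.** Section 3.8.2 states that the percentage below 50 copies/mL "will be displayed on Day 11 (last value prior to starting standard of care". Section 6.3 likewise treats Day 11 as the last visit before SOC is added. Section 7.1.7.1 summarises "events with an onset date up to Day 11 (prior to adding SOC", and Section 7.2.2.2 describes laboratory abnormalities up to Study Day 11 as preceding SOC.

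**The rule.** Section 3.8.1: "Study day will be calculated from the first dosing date of study drug". Table 3-1 then assigns HIV-1 RNA by study day: the Day 11 window is Day 11 only, and everything from Day 12 onward goes to Day 25. Section 3.8.3 adds: "For baseline and postbaseline HIV-1 RNA, the latest (considering both date and time) record(s) in the window will be selected". The SOC start date appears in none of these rules, nor in Sections 6.1 to 6.4 as a condition on which records are used.

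**Early discontinuation.** Appendix 1, footnote q: "Participants who discontinue study drug before Day 11 should start this regimen at the time of discontinuation". Footnote c: "ET assessments will be performed within 72 hours of prematurely discontinuing from the study or study drug, as applicable". The ET column of that table includes plasma HIV-1 RNA.

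**The concern.** The label and the rule agree only for a participant who attends on Day 11 and starts SOC after that visit's assessments. For someone who stops GS-6212 sooner, the calendar rule keeps collecting data under the monotherapy heading after a full regimen has begun. The response to that regimen would be credited to GS-6212, in a single cohort planned at 6 to 8 participants and compared with historical placebo. If the full regimen lowers HIV-1 RNA further, the error favours the drug. For safety, events and laboratory changes that begin on BVY/SOC would appear in summaries presented as pre-SOC.

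**Working it through.** The SAP gives no figure on this point, so there is none to reproduce. The check maps dates to windows and then does a simple mean-shift calculation.

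**Inputs**
- GS-6212 dosing: Days 1 to 10 (Section 4.2.1; Appendix 1, footnote o).
- SOC start after an early stop: at discontinuation (footnote q).
- ET sample: within 72 hours of discontinuation (footnote c).
- Windows: Day 8 is Day 8 only; Day 11 is Day 11 only (Table 3-1). Maximum reduction runs from Day 2 to Day 11 (Section 6.3). Ever below 50 copies/mL runs from postbaseline to Day 11 (Section 6.2.2).
- Population: FAS, all dosed participants (Sections 3.1.2 and 6.1).
- Cohort size 6 to 8 and target difference 1.0 log10 (Section 1.3).

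**Step 1: which stops reach which endpoint.** If study drug stops on Day d, the ET sample can fall on Days d to d + 3.

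| Analysis | Condition | Stop days that can contribute an on-ART value |
|---|---|---|
| Day 11 change (primary) | d ≤ 10 and d + 3 ≥ 11 | 8, 9, 10 |
| Day 8 change (secondary) | d ≤ 8 and d + 3 ≥ 8 | 5, 6, 7, 8 |
| Maximum reduction; ever < 50 copies/mL | some day in d to d + 3 lies in Days 2 to 11 | 1 to 10 |

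Where the ET sample falls on the day of the stop itself (for example, a stop and a sample both on Day 8), it is on-ART only if SOC was taken before the draw.

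**Step 2: does anything remove these values?** Section 6.4 excludes under-dosed participants and early terminators, but only from sensitivity analyses of Day 11 change, maximum reduction and change by visit. The last of these would show Day 8 descriptively. The Day 8 test, the ever-below-50 analysis and the AE and laboratory summaries have no such version, and the FAS primary analysis is unchanged.

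**Step 3: size for HIV-1 RNA.** If one participant's value is lower by x because of SOC, the cohort mean moves by x/n. The SAP gives no x; 0.25 to 1.0 log10 is an assumed range.

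| x (log10) | n = 6 | n = 8 |
|---|---|---|
| 0.25 | 0.25/6 = 0.042 | 0.25/8 = 0.031 |
| 0.5 | 0.5/6 = 0.083 | 0.5/8 = 0.063 |
| 1.0 | 1.0/6 = 0.167 | 1.0/8 = 0.125 |

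For ever below 50 copies/mL, one participant is 1/6 = 16.7 or 1/8 = 12.5 percentage points.

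**Step 4: safety.** An AE or laboratory change after an early SOC start but no later than Day 11 meets the calendar rule and contradicts its label. For AEs this does not even need an early stop. Completers start SOC on Day 11 after assessments, so an AE with onset later that day also falls under the up-to-Day-11 heading.

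**The case against.** Several counter-arguments carry weight.

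- **Contamination of the primary endpoint needs a chain of events:** a stop on Days 8 to 10, SOC taken before the ET draw, and a draw on Day 11. Footnote q also says SOC begins after Day 11 assessments or upon ET, and it refers to a master protocol section not at hand, so some ET samples may precede SOC. This limits the likelihood. The 72-hour allowance still means the order is not assured.
- **The pre-SOC parentheses could be read as limiting the data.** They show intent, but give a programmer no derivation.
- **Section 6.4 would reveal the effect on the primary result.** That is true for Day 11 change and maximum reduction, but not for the other analyses listed in Step 2.
- **Section 4.2.1 documents SOC start dates, not times,** and its eCRF sentence names only BVY. Any fix therefore needs a same-day convention. The same section computes duration on alternative SOC from its first dose date, so that date is expected to exist.

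A reader might infer three stronger points that the SAP does not support.

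- **That a pre-SOC sample drawn on Day 12 is wrongly lost.** Section 3.8.2 does say "Participant visits might not occur on protocol-specified days", but a one-day window is a defensible choice for an endpoint defined on Day 11. Dosing ends on Day 10, and a window open until SOC starts would admit increasingly off-drug values. The Day 12 value would also rarely be reported as Day 25, because the latest record in that window is the one used.
- **That such a loss cuts power from 83% to 72%.** That is unequal-variance design power at n = 6 against n = 5. It depends on a late visit that nothing in the SAP shows.
- **That the latest-record rule favours post-SOC values.** In a one-day window it matters only if there is a second draw that day.

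**Conclusion.** The concern holds as a mismatch between a stated label and the rule that implements it. As written, on-ART HIV-1 RNA can enter the FAS Day 11, Day 8, maximum-reduction and ever-below-50 analyses, and on-ART safety data can be reported as pre-SOC. The size is conditional: about 0.03 to 0.17 log10 in the cohort mean for one affected participant, against a target difference of 1.0. This rests on an assumed extra decline of 0.25 to 1.0 log10 and on at least one early stop with sampling after SOC starts. The SAP does not show that any participant was affected. It is worth correcting because the expected direction favours the drug, the cohort is small and the date needed is already collected.

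**What to change.** **Section 3.8.2.** State that HIV-1 RNA collected after the BVY/SOC start date is excluded from all through-Day-11 analyses: Sections 6.1 and 6.2, maximum reduction, change by visit and the Day 11 display in 6.3, and Section 6.4. Add a same-day convention, since only dates are documented. For example, a scheduled Day 11 or ET sample taken on the SOC start date counts as pre-SOC. This convention only assigns data for analysis; it does not touch when treatment starts. Keep the one-day Day 11 window.

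**Sections 7.1.7.1 and 7.2.2.2.** End the period labelled as pre-SOC at the earlier of Day 11 and the BVY/SOC start date, and state how events and laboratory values dated on the start date itself are classified.

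**Cost.** A few sentences and a flag derived from the SOC start date, after confirming that the date is held for alternative SOC as well as BVY. Because the SAP is signed, Section 1 would require a later change to be documented in the CSR. The main downside is that an early terminator may have no Day 11 value in the primary analysis; the number of such participants should be reported beside the result.
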